6.9 Management of Adverse Events of Special Interest

Adverse events of special interest (AESI) are serious or nonserious AEs specific to the known mechanism of action of the study intervention that are of clinical interest.

For this study, AESIs include the following:

- Infusion-related reactions including hypersensitivity
- Immune-related AEs

- TGF- β inhibition mediated skin reactions
- Anemia
- Bleeding AEs

6.9.1 Infusion-related Reactions Including Hypersensitivity

Infusion-related reactions, including hypersensitivity, are defined in this section. Infusion-related reactions are AESIs and identified risks for bintrafusp alfa.

Infusion-Related Reactions

Infusion-related reactions are defined as any signs or symptoms experienced by participants during the infusion of pharmacologic or biologic agents or any event occurring during or within 1 day of study intervention administration. They are identified based on a list of Medical Dictionary for Regulatory Activities (MedDRA) preferred terms and criteria on the timely relationship to an infusion. Events are divided into reactions versus signs and symptoms:

- Reactions are considered when onset is on the day of infusion (during or after the infusion) or the day after the infusion (irrespective of resolution date) for IRR, drug hypersensitivity, anaphylactic reaction, hypersensitivity, and Type 1 hypersensitivity.
- Signs and symptoms of IRR and hypersensitivity/allergic reactions are considered when onset is on the day of infusion (during or after the infusion) and resolved completely with the end date within 2 days after onset of (but not limited to) pyrexia, chills, flushing, hypotension, dyspnea, wheezing, back pain, abdominal pain, and urticaria.

Management of Infusion-Related Reactions

Premedication prior to bintrafusp alfa administration is optional and at the discretion of the Investigator. If an Investigator chooses to administer premedications, premedication with an antihistamine and with paracetamol (acetaminophen) (e.g., 25 to 50 mg diphenhydramine and 500 to 650 mg paracetamol [acetaminophen] intravenous or oral equivalent) approximately 30 to 60 minutes prior to each dose of bintrafusp alfa is recommended.

If Grade \geq 2 IRRs are seen during the first 2 infusions, premedication should be continued/implemented for future infusions.

An assessment for possible IRR should be triggered based upon the development of specific symptoms within 24 hours of an infusion.

Management of symptoms should follow the guidelines as shown in [Table 5](#).

Table 5

Treatment Modification of Bintrafusp alfa for Symptoms of Infusion-Related Reactions Including Hypersensitivity

NCI-CTCAE v5.0 Grade	Treatment Modification
Grade 1 – mild 
 Mild transient reaction; infusion interruption not indicated; intervention not indicated. 	
 Increase monitoring of vital signs as medically indicated as long as participants are deemed medically stable by the attending Investigator.
Grade 2 – moderate 
 Therapy or infusion interruption indicated but if responds promptly to symptomatic treatment (e.g., antihistamines, NSAIDs, narcotics, IV fluids); prophylactic medications indicated for ≤ 24 hours. 	
 Stop the infusion of the study intervention caused IRR. Increase monitoring of vital signs as medically indicated as participants are deemed medically stable by the attending Investigator. If symptoms resolve quickly or decrease to Grade 1, resume infusion at 50% of original rate with close monitoring of any worsening, otherwise dosing held until resolution of symptoms with mandated premedication for the next scheduled visit. If worsens to Grade 3 or 4, follow treatment modification guidelines accordingly.
Grade 3 or Grade 4 – severe or life-threatening 
 Grade 3: Prolonged (e.g., not rapidly responsive to symptomatic medication and/or brief interruption of infusion); recurrence of symptoms following initial improvement; hospitalization indicated for clinical sequelae. Grade 4: Life-threatening consequences; urgent intervention indicated. 	
 Stop the infusion of study intervention caused IRR immediately and disconnect infusion tubing from the participant with additional appropriate medical measures and closely monitor until deemed medically stable by the attending Investigator. Hospitalization and/or close monitoring is recommended. Administration of glucocorticoids may be required. Restart the medication taking out the drug that is the cause of IRRs from the next scheduled visit.

IRR=infusion-related reaction, IV=intravenous, NCI-CTCAE=National Cancer Institute Common Terminology Criteria for Adverse Events, NSAID=nonsteroidal anti-inflammatory drug.
 
Once the bintrafusp alfa infusion is interrupted or rate reduced to 50% of previous infusion rate, it must remain decreased for all subsequent infusions. For Grade 3 or 4 IRRs, bintrafusp alfa discontinuation is mandated.
 
For all types and grades of infusion reactions, details about drug physical constitution, method of preparation, and infusion must be recorded.
	

In the event of a Grade 2 IRR that does not improve or worsens after implementation of the treatment modifications indicated in Table 5 (including reducing the infusion rate by 50%), the Investigator may consider treatment with corticosteroids and the infusion should be stopped for that day. At the next infusion, the Investigator may consider the addition of H2 blocker antihistamines (e.g., famotidine or ranitidine), in addition to the above provided recommended optional premedication regimen, for selected participants. However, prophylactic steroids are not permitted. At the next dose, if the participant has a second IRR Grade ≥ 2 on the slower infusion rate, with the addition of further medication to premedication, the infusion should be stopped, and the Investigator may consider withdrawal of this participant from the study intervention.

Hypersensitivity Reaction

If a hypersensitivity reaction occurs, the participant must be treated according to the best available medical practice. A complete guideline for the emergency treatment of anaphylactic reactions according to the Working Group of the Resuscitation Council United Kingdom and can be found at <https://www.resus.org.uk/pages/reaction.pdf>. Participants should be instructed to report any delayed reactions to the Investigator immediately.

Symptoms may include, but are not limited to:

- Impaired airway
- Decreased oxygen saturation (< 92%)
- Confusion
- Lethargy
- Hypotension
- Pale/clammy skin
- Cyanosis

Management of hypersensitivity includes:

- Epinephrine injection and intravenous dexamethasone.
- Participant should be placed on cardiac, blood pressure, heart rate, and oxygen saturation monitoring immediately.
- Alert intensive care unit for possible transfer if required.

Prophylaxis of Flu-Like Symptoms

For prophylaxis of flu-like symptoms, a nonsteroidal anti-inflammatory drug, e.g., ibuprofen 400 mg or comparable nonsteroidal anti-inflammatory drug dose, may be administered 2 hours before and 8 hours after the start of each intravenous infusion.

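### Section 6.9.1: the paragraph after Table 5 conflicts with the table's mandatory stop for Grade 3 or 4 infusion reactions in two places

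*Protocol*

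**What the plan says.** All of this text is in Protocol Section 6.9.1.

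- **Table 5, Grade 2.** The reaction calls for interruption but responds promptly to symptomatic treatment. The half rate is conditional: "If symptoms resolve quickly or decrease to Grade 1, resume infusion at 50% of original rate with close monitoring of any worsening". If that condition is not met, "otherwise dosing held until resolution of symptoms with mandated premedication for the next scheduled visit". The row ends: "If worsens to Grade 3 or 4, follow treatment modification guidelines accordingly".
- **Table 5, Grade 3.** The definition includes a reaction that is "not rapidly responsive to symptomatic medication and/or brief interruption of infusion); recurrence of symptoms following initial improvement".
- **Table 5, Grade 3 or 4 action, and the note.** The causative drug is left out from the next scheduled visit, and the note states: "For Grade 3 or 4 IRRs, bintrafusp alfa discontinuation is mandated". The note also says of a reduced rate that "it must remain decreased for all subsequent infusions".
- **Paragraph after the table.** It opens "In the event of a Grade 2 IRR that does not improve or worsens after implementation of the treatment modifications indicated in Table 5" and continues "including reducing the infusion rate by 50%), the Investigator may consider treatment with corticosteroids and the infusion should be stopped for that day". It then describes the next infusion, with an optional H2 blocker added to premedication. If a second IRR of Grade 2 or higher occurs at the slower rate, the infusion is stopped and the Investigator may consider withdrawal.

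Section 6.8 refers IRR guidance to Section 6.9.1. Its own general rules require permanent discontinuation for Grade 4 treatment-related events, and for Grade 3 treatment-related reactions that recur, each with listed exceptions. IRR as such is not among them, although transient Grade 3 flu-like symptoms or fever may be excepted.

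**The concern.** The note makes stopping compulsory at Grade 3 or 4. The paragraph that follows leaves withdrawal optional over a grade range that includes 3 and 4. It also provides for re-dosing after an event that Table 5's own definition can place at Grade 3.

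Two Investigators could therefore treat the same participant differently. One follows the note and stops bintrafusp alfa. The other follows the paragraph and gives the next infusion two weeks later. The second course re-exposes someone whom the note says must stop. IRRs are a listed adverse event of special interest, so the instruction should have only one reading.

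**Working it through.** The check is mainly a comparison of rules. The plan states no figure of its own to reproduce.

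**Step 1: reach of the second-IRR sentence.** Grade 2 or higher means Grades 2, 3 and 4. For Grade 2, optional withdrawal conflicts with nothing. For Grades 3 and 4, it contradicts the note. At Grade 4 it also contradicts Section 6.8. At Grade 3 it contradicts Section 6.8 only if the reaction is a recurrence of a Grade 3 reaction and no listed exception applies.

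**Step 2: symptoms that return at the half rate.** The half rate is available only after quick resolution or a fall to Grade 1. If symptoms resolved and then came back during the same infusion, they recurred after initial improvement. That is one limb of the Grade 3 definition, so the note requires discontinuation. The paragraph speaks of worsening, not returning, so one inference is needed. The resumption condition supplies it when symptoms had fully resolved.

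**Step 3: each case under both rules.**

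| Event | Table 5 and note | Paragraph | Result |
|---|---|---|---|
| Resolved, resumed at 50%, returned in the same infusion | Grade 3, discontinue | Can be read as Grade 2: stop for the day, re-dose | Conflict |
| Fell to Grade 1, resumed at 50%, rose to Grade 2 | May still be Grade 2 | Stop for the day, re-dose | Ambiguous |
| Does not improve | Grade 2 if the response was prompt but incomplete; Grade 3 if not rapidly responsive | Stop for the day, re-dose | Ambiguous |
| Second IRR on the slower rate, Grade 2 | No mandatory stop | Withdrawal optional | Consistent |
| Second IRR on the slower rate, Grade 3 or 4 | Discontinue | Withdrawal optional | Conflict |

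**Step 4: frequency.** Inputs are the related-IRR rate below 5% (Section 2.3) and 29 planned participants. At the 5% boundary, treating participants as independent:

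- Expected participants with any related IRR: 0.05 × 29 = 1.45.
- P(none) = 0.95^29 = 0.226, so P(at least one) = 1 − 0.226 = 0.774.
- P(exactly one) = 29 × 0.05 × 0.95^28 = 0.345.
- P(two or more) = 1 − 0.226 − 0.345 = 0.43 (rounded).

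These figures are for any related IRR. The documents do not give the share that is of the contested type. If that share is s, the expected number affected is below 1.45 × s, which runs from 0 (s = 0) to below 1.45 (s = 1).

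**The case against.** The strongest reply is that the text can be harmonised. The paragraph is confined to Grade 2 by its opening words, the Grade 2 row sends worsening to the Grade 3 or 4 instructions, and the note has no exceptions. A reaction recognised as Grade 3 or 4 is therefore already stopped. The paragraph also has a legitimate scope: a reaction that responded promptly but is still Grade 2, or a new Grade 2 reaction at a later infusion.

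Much of this stands. A reader might infer that every reaction that fails to improve or worsens under the paragraph is a Grade 3 event being re-dosed. The documents do not support that. Failure to improve can describe a prompt but incomplete response, just as the Grade 2 row's hold-and-premedicate branch can. Residual Grade 1 symptoms that rise to Grade 2 never went away, so the recurrence limb need not apply.

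The reply does not remove the two conflicts. Redirection to the Grade 3 or 4 row works only if the event is regraded, and the paragraph keeps the Grade 2 label while giving its own action for worsening at the half rate. The second-IRR sentence names a range that extends above Grade 2, so its opening limit to Grade 2 does not help there.

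Other safeguards reduce the risk. Section 7.1 lets the Investigator stop treatment at any time for safety, and a reduced rate must be kept.

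**Conclusion.** The point holds in a limited form. The second-IRR sentence contradicts the note at Grades 3 and 4 as worded. For symptoms that resolve and then return within one infusion, the paragraph can be read against the note. The other cases are ambiguous.

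The practical size is small. Section 2.3 reports related IRRs as typically Grade 1 or 2 and not requiring permanent discontinuation, so the contested share is probably low, but it is unknown. A reader might take 1.45 of 29 as a ceiling on affected participants. It is an expected count at the 5% boundary, and two or more participants with a related IRR would then have probability of about 0.43. The calculation assumes that the Phase I rate carries over and that 29 are treated. SAP Section 4.1 records early discontinuation with a low number of participants, so the realised exposure is likely smaller.

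A reader might also infer a threat to the primary result. The response definition, analysis set and confidence interval method do not depend on this text. This is a minor participant-safety correction.

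**What to change.** Make two wording changes in the paragraph after Table 5.

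1. Add at the start: *This paragraph applies only to reactions that remain Grade 2 by the Table 5 definition. Any IRR meeting the Table 5 Grade 3 or 4 definition, including symptoms that return during the same infusion after resolving, is discontinued per the Table 5 note.*
2. Replace the second-IRR rule with: *Second Grade 2 IRR at a later infusion on the slower rate: stop the infusion; the Investigator may consider withdrawal. Grade 3 or 4: discontinue per the Table 5 note.*

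The two parts separate a same-infusion return of symptoms from a new Grade 2 reaction at a later infusion.

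The cost is amendment wording in one paragraph, with no added visits, procedures or participants and no SAP change. There is also a clinical cost. Participants whose symptoms return in the same infusion lose the premedicated rechallenge, except through the reinitiation route in Section 7.1.2.1. That route needs the Medical Responsible's agreement, a benefit-risk confirmation and a new baseline scan. If the sponsor wants to keep the rechallenge for this group, it should narrow the note explicitly instead.

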6.9.2 Immune-related Adverse Events

Immune-related AEs are specific to immunotherapies and vary by organ system. Immune-related AEs are considered AESIs.

In general, the spectrum of irAEs is similar for bintrafusp alfa compared with other checkpoint inhibitors. Effective risk management of these toxicities (irAEs) primarily caused due to inhibition of PD-L1 and PD-1 pathways is based on key recommendations (Champiat 2016). Participant education for on-time reporting of symptoms of potential irAEs and prompt clinical assessment is critical for effective management and quicker resolution of immune-mediated toxicities, thus preventing progression into severe forms of toxicity that otherwise may become life-threatening and difficult to manage or warrant permanent discontinuation from the study.

The following irAEs are important identified risks for bintrafusp alfa

- Immune-related hepatitis
- Immune-related pneumonitis
- Immune-related colitis
- Immune-related nephritis and renal dysfunction
- Immune-related endocrinopathies (thyroid disorders, adrenal insufficiency, Type 1 diabetes mellitus, pituitary disorders)
- Immune-related rash
- Other immune-related events (myositis, myocarditis, encephalitis).

The following irAEs are important potential risks for bintrafusp alfa:

- Guillain-Barré syndrome
- Uveitis
- Pancreatitis
- Myasthenia gravis/myasthenic syndrome.

The Medical Monitor may be involved as needed for follow-up. Details of the diagnostic work-up will be requested by the study team.

Recommended guidance and management for specific irAEs as per published guidelines are provided in [Appendix 5](#). These recommendations are in accordance with the joint ASCO Clinical Practice Guidelines ([Brahmer 2018](#)) and National Comprehensive Cancer Network ([NCCN 2018](#)) guidelines.

Treatment of irAEs is mainly dependent upon severity as defined by NCI-CTCAE v5.0. In general, management by NCI-CTCAE v5.0 grading is listed below:

- Grade 1: study intervention should be continued with close monitoring, with the exception of some neurologic, hematologic, and cardiac toxicities.
- Grade 2: study intervention may be suspended for most Grade 2 toxicities, with consideration of resuming when symptoms revert to Grade 1 or less. Corticosteroids may be administered (initial dose of 0.5 to 1 mg/kg/day of prednisone or equivalent).
- Grade 3: study intervention is generally suspended and the high-dose corticosteroids (prednisone 1 to 2 mg/kg/day or methylprednisolone 1 to 2 mg/kg/day) treatment should be initiated. Corticosteroids should be tapered over the course of at least 4 to 6 weeks. Some refractory cases may require infliximab or other immunosuppressive therapy.
- Grade 4: in general, permanent discontinuation of study intervention is recommended, with the exception of endocrinopathies that have been controlled by hormone replacement.

Permanent treatment discontinuation is required in case of immune-related Grade 4 rash/inflammatory dermatitis, nephritis, autoimmune hemolytic anemia, hemolytic uremic syndrome, aplastic anemia, immune thrombocytopenia, acquired thrombotic thrombocytopenic purpura, inflammatory arthritis, myositis, and polymyalgia-like syndrome.

For Grade 4 immune-related lymphopenia, permanent treatment discontinuation will be required, if lymphopenia is considered immune-related in nature, no clear alternative explanation exists for the event, and Grade 4 lymphopenia does not resolve within 14 days. Permanent treatment discontinuation is not required when the AE is manifested by a single laboratory value out of normal range without any clinical correlates. In this case, treatment should be held until the etiology is determined. If the event is not considered immune-related and resolves to Grade ≤ 1 , restarting treatment may be considered.

For Grade 1 immune-related pneumonitis: continue treatment. If clinically indicated, monitor participants weekly or more frequently as needed with history, physical examination, and pulse oximetry. If symptoms appear and/or changes in the physical examination are noted, treat as Grade 2.

For myositis: in case of management with rituximab, treatment should be discontinued.

For organ/system specific management guidelines, see the guideline tables in [Appendix 5](#).

Recommended guidance and management for specific irAEs are provided in the current NCCN guideline available at <http://www.nccn.org>.

6.9.3 TGF- β Inhibition Mediated Skin Reactions

TGF- β inhibition mediated skin reactions, including hyperkeratosis, KA, and/or cSCCs, are important identified risks and AESI for bintrafusp alfa.

Skin assessments are performed at Screening and every 6 weeks for all participants per Schedule of Activities ([Table 1](#)). Baseline skin assessments include a detailed medical history of genetic or iatrogenic skin conditions, skin type, significant UV exposure/sun damage of skin, geographical location, and occupational or environmental exposure to radiation or chemicals.

Skin AEs appear to be related to both mechanisms of bintrafusp alfa; anti-PD-L1 and anti-TGF- β :

1. Immune-related skin AEs possibly mediated by PD-L1 inhibition (e.g., rash or maculo-papular rash, distributed typically on trunk and uniformly on limbs).

Immune-related skin AEs should be managed according to the recommended guidance and management for specific irAEs as per published guidelines (see [Appendix 5](#)). Treatment typically include use of emollients, non-sedating antihistamines for pruritus, targeted use of potent topical steroids to most inflamed lesions; oral corticosteroids in highly symptomatic case.

2. Skin AEs, possibly due to TGF- β inhibition, including hyperkeratosis, KA and/or cSCC, are important identified risks for bintrafusp alfa. The distribution of lesions tends to be in sun-exposed areas.

Management guidelines for potential TGF- β inhibition mediated skin reactions are:

1. Discontinuation or interruption is not required in most cases. Continuation of treatment should be evaluated by the Investigator.
2. Emollients may continue to be used.
3. Diagnostic and treatment plan should be developed in collaboration between Investigator and dermatologist. In general, treatment of TGF- β inhibition mediated skin lesions such as hyperkeratosis, KA and cSCC should be based on local guidelines/standard of care. Lesion evaluation should include excision biopsy of one representative lesion to confirm diagnosis.
4. Treatment and follow-up for KA and cSCC will depend on number and localization of lesions.
 - For single lesions: Full excision may be recommended.
 - In case of multiple lesions or location not suitable for full excision, other treatment options may be offered by the dermatologist, such as:
 - Mohs surgery, cryotherapy, or other standard treatment options depending on the pathology.
 - Use of retinoids, if recommended by dermatologist, may be considered after discussion with Medical Monitor.
5. Close clinical follow-up for re-evaluation, resolution, or potential recurrence should be implemented.
6. Spontaneous resolution of KA lesions without surgical intervention has been observed, typically occurring within weeks after discontinuing bintrafusp alfa.
7. The number and localization of lesions, diagnosis (including histopathological diagnosis), treatment, and outcome should be appropriately documented in the eCRF.

Consult with study Medical Monitor, as needed, for management of TGF- β inhibition mediated skin reactions.

6.9.4 Anemia

Anemia is an AESI (refer to IB) and important identified risk for bintrafusp alfa. Notably, there are many reasons for anemia in patients with advanced cancer, therefore, a thorough investigation of new anemia cases of unspecified etiology is requested.

For new anemia events, items queried may include, but are not limited to, detailed relevant past medical and treatment history, bruising tendency, history of blood transfusions and/or dependency, and a request for an updated eCRF including details such as concomitant medications, all laboratory data, updated dosing information and, recent tumor evaluation scans.

General guidance for anemia management and evaluation:

- Participants must enter the study with Hgb values at least 9 g/dL; routine blood test parameters are required as in the Schedule of Activities (Table 1).
- All relevant hematologic testing for anemias should be done prior to a blood transfusion, if clinically feasible.
- Transfusion should be performed at the discretion of the Investigator based on clinical assessment and considered when the participant experiences significant anemia. An attempt should be made to initiate work-up (as specified below) for the cause of anemia prior to transfusion, if clinically feasible, to not confound this work-up. In general, blood transfusions and erythroid growth factors are permitted as clinically indicated.

Guidance for evaluation of suspected anemias is provided in Table 6.

Table 6 Evaluation Guidance of Suspected Anemia Adverse Events

Baseline Anemia Evaluation (Prior to Transfusion, if feasible)	
CBC with differential (e.g., Hgb, hematocrit, MCV, reticulocytes counts, ANC). Peripheral blood smear for cell morphological assessment. Complete metabolic panel including liver panel-LFTs, bilirubin, LDH, renal function, and other chemistries, if indicated:	

 1. Coagulation factors (PT, PTT, INR) 2. Urinalysis including culture 3. Iron panel (TIBC, ferritin, Fe) 4. Serum folate, B12 values 5. TSH/hormonal panel 6. Fecal-occult blood testing 7. Erythropoietin 	
Further Recommendation Based on Suspected Etiology (in Addition to Baseline Anemia Testing)	
Unknown etiology, suspect possible hemolysis	Coombs test, fibrinogen, haptoglobin, d-dimer. Consider hematology consultation. Consider blood transfusion at clinical discretion.
Unknown etiology, suspect possible bleeding	Consider blood transfusion at clinical discretion. Consider surgical/interventional radiology consultation. Consider imaging, as clinically indicated (e.g., FAST scan, CT scan, MRI, angiography). Consider endoscopy (upper/lower).
Unknown etiology despite above work-up	Hematology consultation. Consider bone marrow aspiration/morphologic evaluation.
ANC=absolute neutrophil count, CBC=complete blood count, CT=computed tomography, FAST=Focused assessment with sonography for trauma, Fe=iron, Hgb=hemoglobin, INR=international normalized ratio, LDH=lactate dehydrogenase, LFT=liver function test, MCV=mean corpuscular volume, MRI=magnetic resonance imaging, PT=prothrombin time, PTT=partial thromboplastin time, TIBC=total iron binding capacity, TSH=thyroid-stimulating hormone.	

